5.3 Treatments Administered

In Part 1 (dose-escalation), each patient will be assigned a dose level as described in Section 3.2. In Part 2 (expansion), all patients will be assigned to the dose level identified in Part 1 by the DESC.

ADCT-402 will be administered on investigational product (IP) administration day of each cycle as a 1-hour IV infusion. If ADCT-402 is well tolerated after the first infusion, the infusion duration may be shortened to 30 minutes for subsequent infusions, on an individual patient basis, at the Investigator's discretion. Variations in infusion times due to minor differences in IV bag overfill/underfill and the institution's procedure for flushing chemotherapy lines will not result in protocol deviation.

Prophylactic antiemetic medications, electrolyte supplementation, and other standard supportive care measures may also be administered according to standard treatment center protocols, or as in Section 5.2 and Section 5.9.2.

Because of non-clinical observations related to nephropathy and adrenal gland changes, adequate patient hydration (e.g., 8 to 10 glasses of water or equivalent per day) is recommended for patients receiving ADCT-402.

New or worsening edema and / or new or worsening pleural effusion have been observed. Therefore patients are advised to monitor their weight on a daily basis (Sections 5.9.2 and 6.3.8).

As non-clinical testing indicates testicular toxicity (atrophy with reduced spermatogenesis), male patients are advised to consider cryopreservation of sperm prior to treatment with ADCT-402, where applicable.

Available pre-clinical data on ADCT-402 does not suggest a photosensitivity concern, based on the lack of any signals in the rat and monkey toxicology studies with ADCT-402 and the

However, skin rash has been reported in another program conducted by this Sponsor, as well as with another investigational agent containing the same pyrollobenzodiazepine warhead (Rudin 2016). The rash has been limited to areas at risk for sun exposure, it is therefore recommended that precautions are taken to avoid prolonged exposure of skin to direct sunlight.

ADC Therapeutics ADCT-402 ADCT-402-102

5.4 Dose Delays and Modifications

Patients will receive the first 2 cycles of ADCT-402, irrespective of blood count recovery. For patients achieving a CR/CRi, the subsequent cycle would be delayed until peripheral blood count recovery (absolute neutrophil count [ANC] $>500 \times 10^9$ /L and/or platelets $>50 \times 10^9$ /L).

The Investigator may suspend ADCT-402 dosing for up to 21 days for any patient who experiences a protocol-defined DLT after Cycle 1 (the defined DLT observation period). At the discretion of the Investigator, the dose may also be delayed for up to 21 days for any toxicity that does not meet DLT criteria. Resumption of dosing with ADCT-402 after suspension is at the discretion of the Investigator, based on assessment of the patient's clinical condition and whether or not the patient is deriving potential clinical benefit from treatment with ADCT-402. Following recovery to Grade 1 or to baseline Grade, treatment with ADCT-402 may resume at the Investigator's discretion.

Patients who resume treatment following a dose delay may, at the discretion of the Investigator, have their dose reduced by 1 dose level. If toxicity recurs at a severity that would mandate a dose delay, then the dose may be further reduced 1 dose level. If toxicity recurs at such level, then the patient is to be discontinued from treatment. Dose re-escalation is allowed at the Investigator's discretion, at maximum to the dose level the patient was initially assigned to.

Dose frequency may be adjusted according to individual patient response as described in Section 3.2.

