ADCT-402-102 Protocol Amendment 3

interruptus), lactational amenorrhea method, and spermicide-only are not acceptable as highly effective methods of contraception.

8. WBC value of <15,000 cells/μL prior to Cycle 1 Day 1.

Exclusion Criteria:

- **1.** Patients who, in the opinion of the Investigator, have an option for other treatment for B-ALL at the current state of disease.
- 2. Known active central nervous system (CNS) leukemia, defined as morphologic evidence of lymphoblasts in the cerebrospinal fluid (CSF), use of CNS-directed intrathecal treatment for active disease within 28 days prior to Screening, or symptomatic CNS leukemia (i.e., cranial nerve palsies or other significant neurologic dysfunction) within 28 days prior to Screening.

Note: Patients may have a history of CNS leukemic involvement if they have received prior treatment for CNS involvement and no evidence of active disease (defined as ≥2 consecutive spinal fluid assessments with no evidence of disease) is present at Screening. Prophylactic intrathecal chemotherapy is not a criterion for exclusion.

- **3.** Patients with Burkitt's leukemia/lymphoma.
- **4.** Active graft-versus-host disease.
- **5.** Autologous or allogenic transplant within the 60 days prior to Screening.
- **6.** Known history of immunogenicity or hypersensitivity to a CD19 antibody.
- 7. Known history of positive serum human ADA.
- **8.** Active autoimmune disease (e.g., rheumatoid arthritis, systemic progressive sclerosis [scleroderma], systemic lupus erythematosus, Sjögren's syndrome, autoimmune vasculitis [e.g., Wegener's granulomatosis]); motor neuropathy considered of autoimmune origin (e.g., Guillain-Barré syndrome and myasthenia gravis); other CNS autoimmune disease (e.g., poliomyelitis, multiple sclerosis).
- **9.** Known seropositive for human immunodeficiency (HIV) virus, hepatitis B surface antigen (HBsAg), or antibody to hepatitis C virus (anti-HCV) with confirmatory testing and requiring anti-viral therapy.

Note: Testing is not mandatory to be eligible. Testing for HCV should be considered if the patient is at risk for having undiagnosed HCV (e.g., history of injection drug use).

- **10.** History of Stevens-Johnson syndrome or toxic epidermal necrolysis syndrome.
- **11.** Pregnant or breastfeeding women.

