6.1 Efficacy Assessments

Assessment of response to treatment with ADCT-402 will be based on bone marrow samples (aspirate, or biopsy if aspirate unattainable). Bone marrow samples will be obtained as described in Section 4.1.2.1.

The activity of ADCT-402 will be evaluated based on the Investigator's evaluation of the patient's response to ADCT-402 as CR, CRi, PR, PD, or NR (Cheson, 2003; Döhner, 2010).

- Complete response is defined as achieving each of the following:
 - o Bone marrow differential showing $\leq 5\%$ blast cells,
 - Absolute neutrophil count $\ge 1.0 \times 10^9 / L$ and platelet count $\ge 100 \times 10^9 / L$,
 - o Absence of extra-medullary disease,
 - o Patient is independent of red blood cell (RBC) transfusions.
- Complete response with incomplete blood count recovery is defined as achieving all CR criteria except that values for ANC may be $<1.0 \times 10^9/L$ and/or values for platelets may be $<100 \times 10^9/L$.
- Partial response is defined as achieving each of the following:
 - o ANC $\geq 1.0 \times 109/L$ and platelet count $\geq 100 \times 109/L$,
 - O Bone marrow differential showing a \geq 50% decrease from baseline in the percentage of bone marrow blast cells to a level >5% and \leq 25%.
- No response is defined as not achieving CR, CRi, or PR.
- PD is defined as:
 - \circ For patients with CR or CRi, the first date of reappearance of blast cells in bone marrow and/or peripheral blood to a level ≥5%, or development of extramedullary disease.
 - o For patients with PR, the first date of an increase in blast cells in bone marrow and/or peripheral blood such that the patient does not continue to meet the criteria for PR.

As defined in Section 7.6.2, DOR and ORR will be defined among responders (CR, CRi, PR); OS and PFS will also be determined.

ADCT-402-102 Protocol Amendment 3

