6.3.5.1 Hematology

The complete blood count (CBC) includes WBC with a 5-part differential, platelet count, hemoglobin, hematocrit, and ANC. Peripheral blasts will be included in the hematology analysis for Part 2 only. If the WBC value is <400 x 10⁶/L, a differential is not required. The coagulation panel must include partial thromboplastin time (PTT) and International Normalized Ratio (INR); prothrombin time (PT) expressed in seconds is optional. Patients taking coumarin-derivative anticoagulants should be monitored closely and their anticoagulant dose adjusted as needed.

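### Protocol 5.4's blood-count rule for re-dosing CR/CRi patients prints an unattainable ANC threshold, and its 'and/or' leaves open whether one or both counts must recover

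*Protocol*

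**What the plan says.** Protocol 5.4 opens by exempting the early cycles: "Patients will receive the first 2 cycles of ADCT-402, irrespective of blood count recovery". It then turns to responders. For a patient who has reached CR or CRi, the "subsequent cycle would be delayed until peripheral blood count recovery (absolute neutrophil count [ANC] $>500" × "10^9$ /L and/or platelets $>50" × 10⁹/L).

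This is the only statement of the rule. The synopsis, the schedule tables and the SAP do not repeat it or say whether one or both counts must recover. It is also the only numerical ANC or platelet threshold for re-dosing, and the eligibility criteria set no minimum for either count.

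Three other places give the scale and the population:

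- **Protocol 6.1, CR.** ANC must be at least 1.0 × 10⁹/L and platelets at least 100 × 10⁹/L.
- **Protocol 6.1, CRi.** This is defined as "achieving all CR criteria except that values for ANC may be $<1.0" × 10⁹/L, with a matching allowance for platelets below 100 × 10⁹/L. Neither count has a lower limit.
- **Inclusion criterion 8.** Before first dosing, patients need a "WBC value of <15,000 cells"/µL.

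**The concern.** The line decides when a responding patient may be dosed again, and it has two separate faults.

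**The value.** An ANC above 500 × 10⁹/L is not a count that a patient can reach, so the ANC condition either blocks every restart or drops out of the rule.

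**The connector.** *And/or* does not say whether one or both counts must recover. CRi is by definition a state in which one or both counts may be low, so the rule is least clear in the patients who most need it.

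An error in either direction has a cost. A lenient reading permits an infusion while one lineage is still low. A strict reading prolongs the delay, and Protocol 4.2.1 requires permanent withdrawal from treatment after a dosing delay of more than 21 consecutive days, unless the Sponsor approves an exception.

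**Working it through.** The threshold is a set value, so there is no calculation in the plan to reproduce. The check is a unit conversion followed by a table of decisions.

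**Inputs.** Restart rule: ANC >500 × 10⁹/L *and/or* platelets >50 × 10⁹/L (5.4). CR criteria: ANC ≥1.0 and platelets ≥100 × 10⁹/L (6.1). WBC ceiling: 15,000 cells/µL (inclusion criterion 8). Cycle length: 21 days. DLT period: 1 cycle (6.3.1).

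**Step 1: scale of the printed value.**

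- 500 × 10⁹/L = 500,000 cells/µL.
- Against the CR criterion: 500 / 1.0 = 500 times.
- Against the WBC ceiling: 15,000 cells/µL = 15 × 10⁹/L, and 500 / 15 = 33.3 times. Neutrophils are only part of the WBC. The ceiling applies before Cycle 1, so this is a comparison of scale only.

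**Step 2: the likely intended value.** 500 × 10⁶/L = 500 cells/µL = 0.5 × 10⁹/L. That is 0.5 / 1.0 = 50% of the CR criterion for ANC. The platelet condition is also 50 / 100 = 50% of its CR criterion. Protocol 6.3.5.1 uses the 10⁶/L unit for another low count: "If the WBC value is <400 x 10⁶/L, a differential is not required". This supports 0.5 × 10⁹/L but does not prove it.

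**Step 3: decisions under each reading** (counts in 10⁹/L).

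| ANC | Platelets | Status by counts | Printed 500, *and* | Printed 500, *or* | 0.5, *and* | 0.5, *or* |
|---|---|---|---|---|---|---|
| 1.0 | 100 | CR | hold | may restart | may restart | may restart |
| 0.8 | 80 | CRi | hold | may restart | may restart | may restart |
| 0.3 | 30 | CRi | hold | hold | hold | hold |
| 0.3 | 60 | CRi | hold | may restart | hold | may restart |
| 0.8 | 30 | CRi | hold | hold | hold | may restart |
| 1.2 | 40 | CRi | hold | hold | hold | may restart |

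With the printed value, *and* holds every patient, including one with full CR counts. *Or* depends on platelets alone. With 0.5, the two connectors agree when both counts pass or both fail, and disagree in the last three rows. Correcting the number alone therefore does not settle the rule.

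**Step 4: who is affected.** At 0.5, counts that meet CR satisfy both conditions on that day. However, Protocol 4.1.2.1 lets marrow sampling after CR/CRi fall to every 3 cycles while dosing continues each cycle. A patient recorded as CR can therefore have lower counts at a later Day 1. The ambiguity reaches CRi patients and those CR patients.

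**Step 5: when it applies.** Two exempt cycles take 2 × 21 = 42 days, so the rule first applies at Cycle 3, nominal Day 43. The DLT period ends at Day 21.

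**The case against.** **The ANC figure may be an error in the PDF text.** This stands in part. A 6 misread as a 9 cannot be ruled out without the source page. The exponent faults visible elsewhere (in the PR criteria in 6.1 and in footnote 13 of Table 7) lose the superscript but keep the digit, so a changed digit would be a different kind of error. The point about the value is conditional on the source page; the point about *and/or* is not.

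**Clinical discretion covers the gap.** Section 5.4 lets the Investigator delay up to 21 days for toxicity and adds: "Following recovery to Grade 1 or to baseline Grade, treatment with ADCT-402 may resume". Section 3.2 lets the Dose-Escalation Steering Committee adjust dose or frequency after CR/CRi, and 4.2.1 allows a Sponsor exception to the 21-day limit. These provisions reduce the harm. They do not give sites a common reading of the rule.

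***And/or* may mirror the CRi definition**, meaning that one waits for whichever lineage is low. This is plausible but not stated. At 0.3 and 60 it gives a hold, as *and* does, so it supports the proposed wording.

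**A reader might infer that the rule cannot be applied at all, or that *or* orders dosing of a neutropenic patient.** Neither holds. Read with *or*, the printed line is a usable platelet-only rule, even if unintended. Meeting a condition that ends a mandatory delay permits the next infusion; it does not compel it.

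**Conclusion.** The rule is wrong as written, on two counts: a decision threshold that cannot be met, and a connector that leaves the decision open. The printed ANC value is 500 times the CR criterion. The unresolved connector changes the decision whenever exactly one count is above its restart threshold.

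The severity is minor to moderate. The documents give no frequency for discordant counts, so no number of affected patients or infusions can be stated. The intended value of 0.5 × 10⁹/L is an inference for the sponsor to confirm.

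A reader might infer that dose-finding or the reported results are compromised. The documents do not support that. The rule first applies at Cycle 3, after the DLT period, so Cycle 1 DLT evaluation and the MTD do not depend on it. SAP 3.3 records early termination before escalation was complete, SAP 4.9 only lists efficacy data, and no SAP output uses this threshold. Exposure summaries will reflect whatever delays were taken, but their definitions are unaffected.

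**What to change.** In Protocol 5.4, replace the condition with: ANC >0.5 × 10⁹/L **and** platelets >50 × 10⁹/L. The sponsor's medical team should confirm the ANC value, and the exponent should be checked against the source page. If that team intends *or*, the line should say so and state whether a minimum ANC applies.

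The cost is one corrected line, with no new data or visits. The small downside of *and* is that it may lengthen delays and bring a responder to the 21-day withdrawal rule in 4.2.1. The existing Sponsor-approved exception, for patients who may still benefit, is available for that case.

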4.2.1 Reasons for Withdrawal/Discontinuation

Patients may withdraw from the study at any time and for any reason, without prejudice to their future medical care, by the Investigator or others at the study site.

A patient may be withdrawn from treatment with ADCT-402 for any of the following reasons:

- Disease progression.
- AE

ADCT-402-102 Protocol Amendment 3

- Withdrawal of consent.
- Major protocol deviation.
- Required treatment delay of >21 days (except in case of potential patient benefit, which must be approved by the Sponsor).
- Non-compliance, including lost to follow-up.
- Pregnancy.
- Other (e.g., development of contraindications).
- The Investigator determines that it is in the best interest of the patient to discontinue the patient's participation in the study.
- Discontinuation of the study by the Sponsor.
- Death.

Patients who experience the following significant toxicities will be immediately and permanently withdrawn from treatment with ADCT-402:

- Any patient who experiences a Grade 3 or higher hypersensitivity reaction (Appendix 12.2), regardless of premedication, during any cycle of treatment
- Any patient who experiences a protocol-defined DLT beyond Cycle 1 (except in the case of potential patient benefit, which must be approved by the Sponsor).
- Any patient who experiences a recurrent Grade 3 or 4 toxicity, excluding hematological toxicity.
- Any patient who requires a dosing delay >21 consecutive days from the planned Day 1 dosing at any time during treatment (except in case of potential patient benefit, which must be approved by the Sponsor).

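### Protocol 5.4 lets the Investigator alone resume dosing after a DLT beyond Cycle 1, where 4.2.1 orders withdrawal unless the Sponsor approves; its second dose reduction also fails to exclude recurrent non-hematologic Grade 3/4 toxicity

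*Protocol*

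**What the plan says.** **Protocol 5.4 (Dose Delays and Modifications).** After a late DLT the first step is a pause: "The Investigator may suspend ADCT-402 dosing for up to 21 days for any patient who experiences a protocol-defined DLT after Cycle 1". Restarting is then dealt with twice: "Resumption of dosing with ADCT-402 after suspension is at the discretion of the Investigator", and "Following recovery to Grade 1 or to baseline Grade, treatment with ADCT-402 may resume at the Investigator's discretion". The Investigator is to weigh the patient's condition and possible clinical benefit. Reducing the dose on restart is optional: "Patients who resume treatment following a dose delay may, at the discretion of the Investigator, have their dose reduced by 1 dose level". The next steps are "If toxicity recurs at a severity that would mandate a dose delay, then the dose may be further reduced 1 dose level" and then "If toxicity recurs at such level, then the patient is to be discontinued from treatment". Re-escalation up to the assigned dose is also left to the Investigator.

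**Protocol 4.2.1 (Reasons for Withdrawal/Discontinuation).** Patients with any of four listed events are to be "immediately and permanently withdrawn from treatment with ADCT-402". The events are Grade 3 or higher hypersensitivity in any cycle, a DLT beyond Cycle 1, recurrent Grade 3 or 4 toxicity other than hematological, and a dosing delay of more than 21 days. The DLT and delay items carry an exception for potential benefit that the Sponsor must approve. The other two carry none.

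**Protocol 5.2** also has patients with Grade 3 or higher hypersensitivity withdrawn, and mentions no exception.

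**SAP 4.2, item 3** lists the same four criteria with the same exceptions and adds a fifth, recurrence of toxicity at the second reduced dose level. A patient who meets a criterion and is not withdrawn counts as an important reportable deviation.

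**The concern.** For one event, a DLT beyond Cycle 1, two sections of the protocol give different default actions and different decision-makers. Under 5.4 the default is a pause of up to 21 days and the Investigator decides on restarting. Under 4.2.1 the default is withdrawal, and only the Sponsor can lift it. A site using 5.4 as its dosing guide could re-dose without approval, and at the dose that produced the DLT, since reduction is optional. The patient would lose a safeguard in the first study of this drug in B-ALL, and the site would incur an important deviation while doing what 5.4 says.

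The reduction steps raise a narrower problem. The severity that triggers the second reduction is not defined (delays in 5.4 are themselves discretionary), and no grade or type of toxicity is excluded. A recurrent non-hematologic Grade 3 or 4 toxicity can therefore be read as leading to a lower dose, when 4.2.1 leads to withdrawal.

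**Working it through.** No formula or stated figure is involved. The check sets the sections side by side, follows each type of event through them, and then looks for text that reconciles them.

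**Step 1. Side by side.**

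| Event | Protocol 5.4 | Protocol 4.2.1 | SAP 4.2 item 3, if not withdrawn |
|---|---|---|---|
| DLT beyond Cycle 1, other than hypersensitivity | Pause up to 21 days; Investigator decides on restart | Withdraw unless Sponsor approves for potential benefit | Important deviation, same exception |
| Grade 3+ hypersensitivity (a DLT under 6.3.1), after Cycle 1 | Not separated from other DLTs | Withdraw, no exception (also 5.2) | Important deviation, no exception |
| Recurrent non-hematologic Grade 3/4 | Not excluded from second reduction | Withdraw, no exception | Important deviation, no exception |
| Recurrent hematologic or lower-grade toxicity | Second reduction allowed | Not covered by the recurrence item | Only recurrence at the second reduced level is listed |

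Rows 1 to 3 conflict. Row 4 does not.

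**Step 2. Who decides.** Section 5.4 names the Investigator 6 times and the Sponsor 0 times, and does not refer to 4.2.1. It does refer to Section 3.2 on dose frequency. Section 4.2.1 has 4 triggers; 2 have a Sponsor exception, so 4 − 2 = 2 have none: hypersensitivity and recurrent non-hematologic Grade 3/4 toxicity.

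**Step 3. Size of the step-down difference.** Suppose both reductions in 5.4 are used.

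- Occurrence 1: delay, reduce one level.
- Occurrence 2: reduce one further level under 5.4; withdraw under 4.2.1 if the event is non-hematologic Grade 3/4.
- Occurrence 3: discontinue under 5.4.

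Difference: 3 − 2 = 1 occurrence, and one further dose level. As an illustration from Protocol Table 1 (Q3W), a patient assigned 150 µg/kg moves to 120 and then to 90. On recurrence at 120, 4.2.1 withdraws, while 5.4 allows 90, which is 90/150 = 60% of the assigned dose.

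**Step 4. Which patients step 3 reaches.** Under 6.3.1 most non-hematologic Grade 3 or higher events are DLTs, so beyond Cycle 1 their first occurrence already falls under row 1 or 2. Row 3 matters mainly for two groups:

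- Grade 3/4 events outside the DLT definition, for example electrolyte imbalance not lasting more than 48 hours, or Grade 3 tumor lysis syndrome without irreversible organ damage. Section 5.4 covers these through "the dose may also be delayed for up to 21 days for any toxicity that does not meet DLT criteria".
- Patients kept on treatment under a Sponsor exception after a first DLT, who then have a recurrence.

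**Step 5. Text that might reconcile the sections.** Protocol 4.2.2 has the Investigator confer with the Sponsor on serious or intolerable AEs; conferring is not approval. Protocol 6.3.1 defines DLTs and deals with those in Cycle 1 (permanent discontinuation), but not with later ones. Protocol 5.2 supports 4.2.1 on hypersensitivity. None of these makes restarting under 5.4 subject to 4.2.1.

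**The case against.** The best reply is that the sections can be read together. Section 5.4 is permissive and never says that approval is unnecessary, whereas 4.2.1 is mandatory. Both can be obeyed: the Sponsor grants the exception, and the Investigator then judges whether and when to restart. Both use a 21-day limit and a benefit test in similar terms, and under 9.6 the Investigator agrees to follow the whole protocol. On this view only a cross-reference is missing.

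Part of this stands. A careful reader can obey both sections, and 5.4 should not be read as cancelling the approval in 4.2.1. But 5.4 gives the same benefit judgement to the Investigator, states it as the rule for restarting, and does not point to 4.2.1. A site has no reason from 5.4 to look further, and the safe result depends on its doing so.

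Other parts of the reply also stand:

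- Optional dose reduction is not itself an inconsistency, because the exception in 4.2.1 is also silent on dose. It shows what is at stake but adds no further conflict.
- A reader might infer that SAP 4.2 itself requires the approval. It does not; it repeats the protocol criteria in order to classify deviations.
- A reader might infer that the step-down as a whole contradicts the withdrawal rules. The SAP lists recurrence at the second reduced level next to the recurrent Grade 3/4 criterion, so the two are meant to coexist. Only the exclusion is missing.

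**Conclusion.** The inconsistency is real and should be fixed. Section 5.4 leaves resumption after a DLT beyond Cycle 1 to the Investigator, where 4.2.1 withdraws the patient unless the Sponsor approves. For Grade 3 or higher hypersensitivity, 4.2.1 does not allow even that. The second reduction in 5.4 lacks an exclusion for recurrent non-hematologic Grade 3/4 toxicity, which amounts to one extra occurrence and one further dose level if both reductions are used. The step-down remains valid for hematologic and lower-grade toxicity.

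This rests on the current wording and on the assumption that sites use 5.4 as their guide to restarting. A reader might go further and infer that patients were wrongly re-dosed, or that the MTD or a reported result is affected. The documents do not support this. How many patients met these criteria is not derivable, Cycle 1 DLT handling and the MTD rule are untouched, and SAP 4.2 already settles how deviations are classified. The prospective effect is small, because SAP 3.3 records that the trial stopped before dose escalation was complete.

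**What to change.** Amend Protocol 5.4 only.

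(a) Replace the discretion to resume after a DLT with: *Resumption after a protocol-defined DLT beyond Cycle 1 requires documented Sponsor approval on grounds of potential patient benefit (Section 4.2.1); otherwise the patient is withdrawn from treatment. Patients with a Grade 3 or higher hypersensitivity reaction in any cycle are permanently withdrawn, with no exception (Sections 4.2.1 and 5.2).*

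The second sentence is needed because Grade 3 or higher hypersensitivity is itself a DLT. Without it, the first sentence would open a Sponsor exception that 4.2.1 does not give.

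(b) Add to the reduction paragraph: *These reductions do not apply to recurrent non-hematologic Grade 3 or 4 toxicity, for which the patient is withdrawn from treatment (Section 4.2.1).*

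Investigator discretion stays for toxicity that does not meet DLT criteria, subject to (b). The cost is three sentences in one section and an amendment with the usual Sponsor and IRB/IEC review (10.2.1). No patients, procedures or SAP changes are added.
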